8 STUDY ADMINISTRATION

8.1 Treatment Assignment Methods

8.1.1 Randomization

Selection and Randomization of schools, therapists and supervisors to intervention conditions:

At least thirty-six schools (potentially up to 41) from mental health agencies will participate in this study. Computerized randomization lists will be generated with random assignment of schools (and therefore, the schools' therapists and supervisors of the agencies participating in this study) to Condition A (FRIENDS/TT), B (CATS/TT), or C (CATS/TT+) with the goal of exposing all agencies to each of the three conditions over the course of the study.

Schools will be stratified according to their size (greater than 625 students (yes/no)). Therefore, a list of 18 schools (including their therapists) will be randomly assigned to the treatment groups and will participate in year 1 of the study (Randomize 1). Schools listed in Randomize 1 will also be used in year 2 while recruiting new therapists and their supervisors (potentially repeat supervisors). We expect this to add 6 new therapists (and their supervisors), per intervention condition, to the study. Schools spanning elementary and middle school grades will run interventions with middle school grades in year 1 and elementary grades in year 2.

From the remaining 18 schools (not randomized yet), a stratified new randomization list will be generated for year two and to be used again in year four (Randomize 2) of the study. As a result, a group of six new therapists and their supervisors (potentially repeat supervisors) per intervention will be recruited for year 3 and a new group of six therapists and their supervisors will be recruited for year 4. Schools spanning elementary and middle school grades will run interventions with middle school grades in year 3 and elementary grades in year 4.

For the 5th year, from the original list of 36 schools using the same stratified randomization method, a new randomization list of schools (Randomize 3) will be generated to recruit a new group of 18 therapists and their supervisors (6 per treatment group). Therefore, a new group of 18 therapists per year (a total of 90 therapists) will participate in this study. Each therapist will participate only one time in this study. In schools spanning elementary and middle school grades, the study conditions will be evenly distributed across grade levels.

The three randomization lists may result in assigning the same supervisors to different treatment groups. This may result in modifying the intervention effect due to the supervisor's knowledge gained by participating in a previous different treatment arm. Therefore, working with the agencies, we will make sure that supervisors will stay in the same support condition (i.e.: A or B; C) they were originally assigned using randomize 1 and randomize 2.

New schools will replace dropped schools by matching stratification variables (size and type).

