Context: Unresolved psychological problems, such as anxiety, affect a significant number of our students and interfere with their ability to attend, actively participate, and prosper in school. This project will expand the capacity of selected mental health agencies to provide services in the participating schools through school therapeutic services (STS). The project will provide enhanced training in evidence-based behavioral health interventions to school-based mental health providers. The services will be implemented by STS Master's level therapists supervised by their mental health agency supervisors (Internal Support), who are in turn supported by the research team (TT) or external consultants (TT+).

Objectives: The purpose of this intervention study is to test the effectiveness of FRIENDS (a program for overanxious children) compared to an adapted version (CATS) and to compare the total cost between the interventions. The study also aims to compare support mechanisms: Train-the-Trainer (TT) to Train-the-Trainer Plus (TT+) for the implementation of CATS and to test mediators and moderators of type of support (TT vs. TT+) on therapist fidelity.

Study Design: This is a 3-arm, parallel group, Type 2 hybrid effectiveness-implementation trial in K-8 schools in Philadelphia over 5 years.

Setting/Participants: Schools within the School District of Philadelphia that have STS programs managed by mental health agencies are potentially eligible for participation. Schools (3-6 per agency) will be chosen for participation. Students who present excessive anxiety in grades 4-8 would be potentially eligible to participate in the interventions offered by the agencies' therapists in their school.

Study Interventions and Measures:

This study is designed to test: a) the effectiveness of an adapted version of a group cognitive behavioral therapy program (CATS) compared to the original version of this program (FRIENDS), and b) the effectiveness of two implementation strategies for CATS: Train-the-Trainer and Train-the-Trainer Plus. CATS is a shorter, more culturally sensitive, focused, and feasible CBT for anxiety in children than FRIENDS. CATS addresses one of the major barriers to implementation (intervention-context fit).

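### Every agency is meant to meet all three arms, but agency enters neither the randomisation nor the endpoint analysis, so the goal is left to chance

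*Combined protocol and SAP*

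**What the plan says.** Section 8.1.1 gives the aim of the allocation: schools are assigned to the three conditions "with the goal of exposing all agencies to each of the three conditions over the course of the study". The restriction placed on the lists is "Schools will be stratified according to their size (greater than 625 students (yes/no". At the end of the same section the stratification variables are described differently: "New schools will replace dropped schools by matching stratification variables (size and type". Type is not defined, and agency appears in neither sentence.

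Three lists are planned:
- Randomize 1: "a list of 18 schools (including their therapists) will be randomly assigned to the treatment groups and will participate in year 1". The same schools are used again in year 2.
- Randomize 2: "From the remaining 18 schools (not randomized yet), a stratified new randomization list will be generated".
- Randomize 3, for year 5: "from the original list of 36 schools using the same stratified randomization method, a new randomization list of schools".

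On numbers, section 8.1.1 says "At least thirty-six schools (potentially up to 41) from mental health agencies will participate in this study", and the Abstract says "Schools (3-6 per agency) will be chosen for participation". The number of agencies is not given. Section 8.1.1 also keeps each supervisor in the support condition first assigned (A or B as one, C as the other).

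The covariates listed at the start of section 6 are student characteristics and therapist experience. The endpoint analyses in section 6.1 contain no agency term; agency appears there only as a column in the qualitative interview matrix.

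**The concern.** A stated design goal has no mechanism behind it. Stratifying by size does nothing to spread an agency's three to six schools over three arms, and the analysis does not make up for that.

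Agencies supply the supervisors and therapists, and the B-C contrast tests a way of supporting supervisors. Agency is therefore a plausible source of variation in fidelity, and it is known before any list is drawn. If it matters, two things are lost: within-agency comparison of the arms in agencies that miss one, and precision in both contrasts.

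**Working it through.** **The plan's own power figures (section 6.3).**
- B-C content fidelity: SE = 10 × √(2/30) = 2.58. The non-centrality is 8/2.58 = 3.10 on 58 df, and power is 86.1% (stated 86%).
- A-B equivalence: SE = 11 × √(2/142) = 1.305. Power is 2Φ(4.20/1.305 − 1.645) − 1 = 88.4%, or 88.2% using the t distribution (stated 88%).

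Both reproduce, and neither contains an agency component.

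**Coverage after Randomize 1 and 2.** Inputs: 36 schools, 12 per arm. Assumption: agencies are unrelated to list and size stratum. For an agency with k schools,

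P(all three arms) = 1 − 3·C(24,k)/C(36,k) + 3·C(12,k)/C(36,k).

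- For k = 3: 1 − 3(2024/7140) + 3(220/7140) = 0.242.
- For k = 6: 1 − 3(134596/1947792) + 3(924/1947792) = 0.794.

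**Coverage including year 5.** This was simulated: 18 of the 36 schools drawn again, 6 per arm. Re-assignment was treated in two ways: free, or counting only schools that stay within A/B or within C, as the supervisor rule would imply if it bound every school.

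| Schools in agency | Misses an arm, Randomize 1+2 | With year 5, free | With year 5, support condition held |
|---|---|---|---|
| 3 | 76% | 46% | 65% |
| 4 | 52% | 25% | 42% |
| 5 | 33% | 13% | 25% |
| 6 | 21% | 6% | 15% |

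The chance that every agency meets all three arms over the whole study, with free re-assignment, is:
- about 0% for twelve agencies of 3;
- about 8% for nine agencies of 4;
- about 11% for a mix of 3, 3, 4, 4, 5, 5, 6, 6;
- about 68% for six agencies of 6.

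**Effect on B-C power.** Let ρ be the share of fidelity variance due to agency (not in the documents; assumed 10%, range 5-20%). Let v be the sum over agencies of the squared difference between an agency's shares of arms B and C. Over the three lists, simulation gives v of about 0.107, and 0.10 to 0.11 across agency mixes. Then

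Var(B − C) = 100 × [(2/30)(1 − ρ) + vρ].

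- ρ = 0.10, lists as planned: 100 × (0.0600 + 0.0107) = 7.07, SE 2.66, power 84.1%.
- ρ = 0.05: power 85.1%.
- ρ = 0.20: power 82.1%. With the largest v (0.113, twelve agencies of 3), Var = 5.33 + 2.26 = 7.59 and power is about 81%.
- Agency balanced and modelled (v = 0): SE 2.52, 2.45 and 2.31, and power 87.8%, 89.5% and 92.6%, at ρ = 0.05, 0.10 and 0.20.

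The 89% at ρ = 0.10 assumes exact balance. A residual v of about 0.022, from leftover schools with no agency term, gives 100 × (0.0600 + 0.0022) = 6.22, SE 2.49 and power 88%.

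**Effect on A-B power.** The formula is the same with SD 11, 142 per arm and v = 0.108, for assumed agency shares of 1, 2 and 5% in the student outcome. The SE is 1.35, 1.39 and 1.51, and equivalence power is about 86, 83 and 75%. With agency blocking and residual v = 0.022 it is about 88, 88 and 87%.

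**The case against.** Two stronger readings are tempting, and the documents do not support either.

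A reader might infer that most small agencies will miss an arm. That is true after the first two lists for agencies of three or four schools. But the goal runs over the whole study, which includes the year-5 list. With free re-assignment, a majority of agencies of every size meet all three arms. A majority miss remains only for three-school agencies, and only if the supervisor rule binds every school. Section 3.2.2 allows A and B staff to enter other conditions but confines C staff to C, and an agency can supply a different supervisor. The truth probably lies between the last two columns of the table.

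A reader might also infer that agency is confounded with arm. Schools are randomised, so agency differences add chance imbalance and variance, not a systematic shift. An agency that misses an arm does not by itself bias a comparison.

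The loss also depends on the comparator. At a 10% agency share, the B-C variance is 18% above a fully blocked design (7.07 against 6.00), but the plan never assumed blocking. Against the planned SE of 2.58, the value of 2.66 is 3% larger.

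The agency share and agency sizes are assumed. Section 5.3 counts 12 supervisors and section 3.3.1 requires at least two per agency. That would mean at most six agencies averaging six or more schools, where coverage is good. Section 3.2.2 expects 36-41 supervisors, so agency size is unsettled.

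A further worry is that arms mixed within an agency invite contamination. This carries little weight, because the plan already intends every agency to have all three arms.

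What remains is that no rule delivers the goal, and agency is absent from the analysis.

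**Conclusion.** The point holds as a worthwhile design and analysis improvement, not as a threat to validity. Under no agency size the Abstract allows is the goal assured. Even in the most favourable case, six agencies of six schools, about one study in three would leave some agency short of an arm.

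Against stated B-C power the shortfall is about 1 to 5 points. Balancing and modelling agency would gain about 3 to 11 points over the lists as planned (88 against 85% at a 5% share, 93 against 82% at 20%). The A-B figures point the same way but depend heavily on the assumed share.

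The coverage figures rest on 36 schools, equal arms, agencies spread at random over lists and size strata, and 18 schools drawn in year 5. The power figures rest in addition on an agency share that the documents do not give. The absence of any agency mechanism rests on the text alone.

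**What to change.** In section 8.1.1, constrain each list not yet used so that arms are balanced within agency as far as school numbers allow. For example, use sets of three schools from one agency, one per arm, with leftover schools in mixed sets. Choose among the balanced allocations using school size, so that size becomes a secondary balancing factor. Where earlier lists are already in use, let the remaining lists give priority to the arms an agency has not met, in line with the supervisor rule.

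In section 6, include agency, or the randomisation set, in the A-B and B-C models.

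Reconcile the two descriptions of the stratification variables in section 8.1.1: define type or remove it, and state the number of agencies and the schools in each.

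The cost is a different list-generation program, one model term and a few degrees of freedom. Size balance becomes looser. Agencies whose school count is not a multiple of three leave remainders. An agency's schools must also be coordinated across the two 18-school lists and with the supervisor rule.

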3.2.2 Total Number of Study Sites/Total Number of Subjects Projected

The study will be conducted in a minimum of 36 (potentially up to 41) public K-8 schools within the School District of Philadelphia and in collaboration with community mental health agencies, contracted by CBH, in the City of Philadelphia. However, not every school will participate during every project year. It is anticipated that schools will participate in 2 project years.

We expect there to be a minimum of 36-41 agency supervisors (one per school at all times). However, there is a 17% drop-out rate of supervisors across agencies. Therefore, depending on supervisor turnover, the number of enrolled supervisors will be comparable. If

all therapists participate once per school year, we'd expect to enroll 90 agency therapists (1 therapist per school (n=18), per year of the study (n=5) = 18x5 = 90). However, given that therapists may run a second intervention group, we could end up with fewer therapists than expected. Yearly therapist drop out in the agencies is 25%. Therefore, depending on therapist turnover within the agencies, the number of enrolled therapists will also be comparable.

Each of the participating mental health agencies will make available extra supervisors and therapists to serve as alternates in case a supervisor or therapist drops out of the study or terminates employment with the agency for any reason. Alternate supervisors and therapists will be invited to attend the initial trainings. If a supervisor/therapist moves to another school within the same study arm, s/he will be allowed to remain in the study and will be treated as a returning supervisor. Supervisors/therapists in conditions A and B who move to a school assigned to a different study arm can participate in the project pending PI review. Supervisors/therapist in condition C who move to a new school assigned to condition A or B will not be allowed to continue in the study due to potential condition contamination. They will be counted as drop outs.

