8.5 Risk-Benefit Assessment

8.6 Recruitment Strategy

In collaboration with CBH (during the grant proposal and start-up phases), the research team has identified the participating mental health agencies. Each agency will facilitate school selection as described in Sections 3.2 & 8.1.1. Supervisors and therapists from the agencies who are embedded within the selected schools will be approached for participation. However, participation is voluntary, so if a supervisor or therapist does not

consent to participate, we will ask a different supervisor/therapist (already in the school) to participate. All student recruitment will be based upon school/STS referrals as noted in Sections 3.1.1. Parents of students who meet screening criteria and who have indicated an interest in our program, will be contacted via telephone by a team member about the study.

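### Dropped schools are replaced by matching on size and an undefined 'type', with no random step and no stated way of assigning or concealing the replacement's arm

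*Combined protocol and SAP*

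**What the plan says.** Section 8.1.1 sets out the main assignment: "Computerized randomization lists will be generated with random assignment of schools" to conditions A, B or C. One stratification factor is given: "Schools will be stratified according to their size (greater than 625 students (yes/no". Randomize 1 serves years 1 and 2, and Randomize 2 recruits for years 3 and 4. The last list keeps the same method: "For the 5th year, from the original list of 36 schools using the same stratified randomization method, a new randomization list of schools (Randomize 3". No second factor appears anywhere in this description.

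The section ends with the rule for schools that leave: "New schools will replace dropped schools by matching stratification variables (size and type". That sentence is the whole of the replacement procedure.

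Three other places bear on it. Section 3.2.2 gives the number of schools as "a minimum of 36 (potentially up to 41) public K-8 schools", without saying what the additional schools are for. Section 8.6 says "Each agency will facilitate school selection as described in Sections 3.2 & 8.1.1". Section 8.2 gives the Biostatistics and Data Management Core a role in randomisation.

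**The concern.** Random assignment of schools is what makes the A–B and B–C comparisons fair. A school brought in by matching has not been through that process unless a random step is added, and none is stated. If the new school fills the vacated place, its arm is fixed before it is chosen. Anyone involved in the choice who knows that arm could, knowingly or not, favour a school with better staffing, more enthusiasm or an easier case mix. Matching on size does not prevent this.

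The plan's own rules give some reason for suitability to depend on the arm. FRIENDS and CATS staff are trained separately (section 3.1.2), so arms are visible. Supervisors and therapists who have served in condition C may not continue in A or B (section 3.2.2), so a candidate school may suit one vacancy and not another.

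The word 'type' is a separate defect. A matching variable that is undefined, and wrongly described as a stratification factor, cannot be applied consistently.

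**Working it through.** **1. Text comparison.**

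| Item | Listed schools (8.1.1) | Replacement schools (8.1.1, last sentence) |
|---|---|---|
| How the school gets its arm | Computerised random list | Not stated; 'replace' suggests the vacant arm |
| Variables used | Size only (more than 625 students, yes/no) | Size and 'type' |
| Random step | Yes | None stated |
| Who selects, and concealment | Computerised list | Not stated |

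Each of the first two lists is used for two years, so a vacancy after the first year of a list belongs to an arm already in operation. That supports the reading that the replacement takes over that arm, but the text does not say so. 'Type' might mean grade span, but that is a guess, and 8.1.1 handles grade span separately by project year.

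**2. Scale.** The plan gives no figure for replacements, so there is none to reproduce. The inputs for an illustration are:

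- Margin ±4.20, SD 11 and 142 students per protocol (section 6.3). The stated 88% power of the two one-sided tests reproduces at 88.2%, so these figures are coherent with each other.
- Therapist-groups per arm: 6 new therapists per condition per year × 5 years = 30 (8.1.1), with one group expected per therapist (3.2.2).
- Each school is expected to take part in 2 project years (3.2.2), so a replacement would serve 1 or 2.
- Assumed, not in the documents: two replacement schools, both in the same arm, that arm being A or B, both deviating in the same direction by 0.3 SD = 0.3 × 11 = 3.3 points.

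Groups supplied: 2 schools × 1 or 2 years = 2 to 4 of 30.

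Shift in arm mean = (groups supplied ÷ 30) × deviation:

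- 2/30 × 3.3 = 0.22 points; 0.22 ÷ 4.20 = 5%
- 4/30 × 3.3 = 0.44 points; 0.44 ÷ 4.20 = 10%

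Range over the assumed deviation:

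| Deviation | Points | Shift, 2 of 30 | Shift, 4 of 30 | Share of 4.20 |
|---|---|---|---|---|
| 0.2 SD | 2.2 | 0.15 | 0.29 | 3% to 7% |
| 0.3 SD | 3.3 | 0.22 | 0.44 | 5% to 10% |
| 0.5 SD | 5.5 | 0.37 | 0.73 | 9% to 17% |

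Replacements in condition C would leave the A–B comparison, to which the margin applies, untouched. They would still bear on B–C.

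**The case against.** The best defence is that the rule is one sentence and is silent rather than wrong. It does not say that a replacement takes over the arm, that anyone chooses it by hand, or that the chooser knows the arm, and the biostatistics core could be handling the step. This is fair as far as it goes: the takeover of the arm is an inference, though the natural one. It does not answer the fact that the only method stated is matching.

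A second defence is section 6, which expects imbalance because schools are randomised. It plans to check student demographics, diagnosis, mental health, academic functioning and therapist experience, and to adjust for differences. This is a partial safeguard that reaches measured case mix and experience. It does not reach unmeasured differences such as readiness or staff commitment.

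Some stronger readings are tempting but not supported:

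- A reader might take the agencies' part in school selection (8.6) to mean that they pick replacements with the arm known. That paragraph opens with the grant and start-up phases. Its reference to 8.1.1 may cover replacements, but no text says so.
- A reader might treat schools 37 to 41 as replacements, giving 5/41 = 12% of schools. The documents give only a range and no school drop-out rate.
- A reader might weight two replacements as 2 of 12 schools in an arm, giving 2/12 × 3.3 = 0.55 points, or 13% of the margin. That overstates the effect, because schools serve about two of the five years and year 5 is randomised afresh.

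**Conclusion.** The point holds as a gap in the assignment procedure plus an inconsistency in the text. Two things are certain: the replacement rule contains no random step and no statement on arm assignment or concealment, and 'type' is named as a stratification variable without being defined or used as one. That replacement schools are not randomised follows only if they take over the vacant arm. It should not be stated as fact that part of the sample is non-random, since the plan neither says this nor shows that any school will drop out.

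The likely effect is small: 0.22 to 0.44 points, 5% to 10% of the margin, under the assumptions of two replacements in the same arm (A or B) and a 0.3 SD deviation in the same direction. Depending on its sign, the shift could make equivalence harder to show or help to hide a real difference. This is a minor, inexpensive correction and no reason to doubt the trial's main comparison.

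**What to change.** Replace the last sentence of section 8.1.1 with a procedure along these lines:

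- The biostatistics core puts eligible reserve schools in random order within each size stratum, using the randomisation software.
- Each reserve school's willingness to take part is confirmed before the arm is revealed, ideally when it joins the list. Without this, a school or agency could still decline once it knows the arm.
- Each vacancy goes to the next accepting school in the stratum, and any school passed over is recorded with the reason.
- 'Type' is deleted, or defined and added to the stratification for any list still to be generated.
- Replacement schools are flagged in the data set, and section 6 gains a sensitivity analysis that excludes them.

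The cost is one reserve list, a short paragraph and a little more analysis. The real downside is that agencies have less freedom to choose which school fills a vacancy.
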